2.4.5.1 Analyses of hypoglycemia

Analyses of hypoglycemia will be performed on the TEAE period as defined in [Section 2.1.4](#). For the purpose of hypoglycemia analyses during the 18-week randomized core treatment period, the TEAE period for 18-week randomized core treatment period is (1) the time from the first administration of the double-blind IMP up to 1 day after the last administration of IMP if the patient discontinued treatment on or before Visit 12 (or Day 126 if Visit 18 date is missing), or (2) the time from the first administration of the double-blind IMP to the administration at Visit 12/Week 18 (or Day 126 if Visit 12/Week 18 date is missing) if the patient remained treated beyond Visit 12/Week 18. Hypoglycemia will be classified as severe hypoglycemia, documented symptomatic hypoglycemia, asymptomatic hypoglycemia, probable symptomatic hypoglycemia or relative hypoglycemia (see [Section 2.1.4.1](#)).

The number (%) of patients with any hypoglycemia, severe hypoglycemia and documented symptomatic hypoglycemia will be summarized respectively by treatment group during the TEAE period, as well as the incidence rate in patient years. Two types of incidence rates will be presented: the number of patients with at least 1 event per 100 patient-years (calculated as the number of patients with at least 1 event / total exposure in 100 patient-years), and the number of events per 100 patient-years (calculated as the total number of events / total exposure in 100 patient-years). Note: here exposure (in days) is the duration of TEAE period, ie, duration of IMP treatment in days +1 (see [Section 2.1.4](#)).

The summary of frequency and incidence rate in patient years for severe hypoglycemia or documented symptomatic hypoglycemia will be provided as appropriate by gender (Male, Female), age group (<50, ≥50 to <65, ≥65 years), race (White, Black or African American, Asian, Other), sulfonylurea use at Week -1 (yes, no).

The number (%) of patients with at least 1 severe hypoglycemia or documented symptomatic hypoglycemia during the TEAE period, as well as the corresponding number of events, will be summarized as necessary by hour of the day for each treatment group, using the following hour intervals: ≥23:00 to <06:00, ≥06:00 to <10:00, ≥10:00 to <14:00, ≥14:00 to <18:00, ≥18:00 to <23:00.

A KM curve will also be provided by treatment group for the time to first severe hypoglycemia or documented symptomatic hypoglycemia during the TEAE period for the entire 52-week double-blind treatment period only (see [Section 2.5.4](#)).

Documented symptomatic hypoglycemia maybe presented by ≤ 70 mg/dL (3.9 mmol/L) and < 54 mg/dL (3.0 mmol/L) respectively, as appropriate.

A listing of patients for all events reported on the dedicated e-CRF “Hypoglycemic event information” page will be provided with each category flagged (ie, severe hypoglycemia, documented symptomatic hypoglycemia, asymptomatic hypoglycemia, probable symptomatic hypoglycemia and relative hypoglycemia).

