11.4.3.2 Analysis of hypoglycemia

The number (%) of patients and rate in patient years (2 types: the number of patients with events or the number of events per 100 patient-years) of all, severe and/or documented symptomatic hypoglycemia, will be summarized by treatment group respectively. In addition, documented

hypoglycemia will also be analyzed by using a threshold of plasma glucose of <54 mg/dL (3.0 mmol/L).

Their pattern of occurrence over time will also be assessed, as appropriate.

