2.4.3.1 Extent of investigational medicinal product exposure

The extent of IMP exposure will be assessed by the duration of IMP exposure.

Duration of IMP exposure is defined as last dose date of double-blind IMP – first dose date of double-blind IMP + 1 day, regardless of unplanned intermittent discontinuations (see Section 2.5.3 for calculation in case of missing or incomplete data).

Duration of IMP exposure will be summarized descriptively as a quantitative variable (number of patients exposed, mean, SD, median, minimum, and maximum). In addition, duration of treatment exposure will also be summarized categorically by numbers and percentages for each of the following categories and cumulatively according to these categories:

- 1 to 28 days,
- 29 to 56 days,
- 57 to 84 days,
- 85 to 126 days,
- 127 to 182 days,
- 183 to 364 days,
- >364 days.

Additionally, the cumulative duration of treatment exposure will be provided, defined as the sum of the duration of treatment exposure for all patients, and will be expressed in patient years.

Number and percentages of patients by final dose at the end of the treatment will also be presented by each treatment group.

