When a patient has more than 1 measurement from the central laboratory for the same laboratory parameter on the same date, the average of the measurements will be used. For the same laboratory parameter, if a patient has more than 1 measurement on different dates for the same

scheduled visit, the value closest to the date of the visit will be used for the scheduled visit. When the values for the same scheduled visit are equidistant, the last value should be used for the scheduled visit. Similar rules will be applicable to a patient who has more than 1 set of measurements for the same vital sign parameter (ie, SBP, DBP, or HR) on the same date.

Time to event analysis

For time to event analysis/KM plot, time to event (eg, treatment discontinuation, rescue therapy, hypoglycemia, etc) is defined as the number of days from the date of the first administration of double-blind IMP (or the date of randomization if not exposed) to the start date of the first occurrence of the event during entire 52-week double-blind treatment period.

Patients who did not experience any event during the entire 52-week double-blind treatment period are considered censored observations. For treatment discontinuation and time to rescue, censoring date is the date of EOT. For time to severe or documented hypoglycemia, censoring date is date of EOT+1 or date of EOS, whichever is the earliest. Date of EOS will be used if date of EOT is not available. Last contact date will be used if date of EOS is not available.

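### The patient-based hypoglycemia rate keeps exposure after the first event in its denominator, so it understates the first-event rate; the effect on the comparison between arms depends on event timing and discontinuation

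*SAP*

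**What the plan says.** Protocol 11.4.3.2 announces two rates ("2 types: the number of patients with events or the number of events per 100 patient-years") and does not define the denominator further. SAP 2.4.5.1 defines it. The patient-based rate is "calculated as the number of patients with at least 1 event / total exposure in 100 patient-years" and the event-based rate is "calculated as the total number of events / total exposure in 100 patient-years". A note in the same section fixes the exposure for both: "here exposure (in days) is the duration of TEAE period, ie, duration of IMP treatment in days +1". SAP 2.4.3.1 counts IMP duration from first to last dose, "regardless of unplanned intermittent discontinuations". Nothing in these rules stops the clock at a hypoglycemic event.

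The rates are planned for any, severe and documented symptomatic hypoglycemia, over the 18-week core period and the full 52 weeks. Subgroup rates for severe or documented symptomatic events are planned by sex, age, race and sulfonylurea use. The section also reports the number and percentage of patients with an event. It adds a time-to-event display ("A KM curve will also be provided by treatment group for the time to first severe hypoglycemia or documented symptomatic hypoglycemia"), produced "for the entire 52-week double-blind treatment period only". SAP 2.5.4 gives its censoring rule: "For time to severe or documented hypoglycemia, censoring date is date of EOT+1 or date of EOS, whichever is the earliest".

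**The concern.** The SAP calls the patient-based figure an incidence rate, and its numerator is in effect a count of first events. A rate of first events needs the time during which a first event could still occur. Here a patient who has an event in week 3 and stays on treatment for 52 weeks contributes one event and a full year.

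Two things are at stake. The reported rate is too low as a first-event rate, and more so the commoner the event. The amount by which it is too low can also differ between arms, so the comparison of sotagliflozin with placebo on a main safety question of an insulin add-on trial may be distorted. Any hypoglycemia could well be common: the background is basal insulin, sulfonylureas are allowed, fasting self-monitoring is required, and a reading of 70 mg/dL or below without symptoms qualifies as an event (SAP 2.1.4.1).

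**Working it through.** The documents state no hypoglycemia rate, so there is no figure of the plan's own to reproduce.

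**Identity.** SAP rate = first-event rate × (time at risk / total exposure). The understatement is therefore 1 − (time at risk / total exposure). It is above zero whenever any patient is exposed after a first event.

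**Size.** Let p be the share of patients with at least one event and T the follow-up in years. Assume a constant hazard and full follow-up for everyone.

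- SAP rate = 100 × p / T.
- First-event rate on time at risk = 100 × [−ln(1 − p)] / T.
- T = 365/365.25 for 52 weeks (364 days plus the one-day extension) and 126/365.25 for 18 weeks.
- p is an assumption, ranged from 1% to 65%.

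At p = 30% over 52 weeks, the SAP rate is 30.0. The time-at-risk rate uses −ln(0.7) = 0.357 and is 35.7. The understatement is 1 − 0.300/0.357 = 15.9%. At p = 1% it is 0.5%. For pairs of arms over 52 weeks, per 100 patient-years:

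| Assumed p, lower v higher arm | SAP rates | Time-at-risk rates | Ratio: SAP → at risk | Understatement by arm |
|---|---|---|---|---|
| 2% v 3% | 2.0 v 3.0 | 2.0 v 3.0 | 1.50 → 1.51 | 1.0%, 1.5% |
| 10% v 15% | 10.0 v 15.0 | 10.5 v 16.3 | 1.50 → 1.54 | 5.1%, 7.7% |
| 20% v 30% | 20.0 v 30.0 | 22.3 v 35.7 | 1.50 → 1.60 | 10.4%, 15.9% |
| 30% v 45% | 30.0 v 45.0 | 35.7 v 59.8 | 1.50 → 1.68 | 15.9%, 24.7% |
| 50% v 65% | 50.0 v 65.0 | 69.4 v 105.1 | 1.30 → 1.51 | 27.9%, 38.1% |

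For a given p, the 18-week ratios and percentage understatements are the same, because T cancels. The absolute gap is wider: at p = 30%, 87.0 against 103.4 per 100 patient-years.

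Read the other way, a true first-event rate ratio of 1.5 would appear as 1.49, 1.46, 1.42, 1.38 and 1.29 when the lower-rate arm has p = 2%, 10%, 20%, 30% and 50%. A true ratio of 0.7 would appear as 0.70, 0.71, 0.72, 0.74 and 0.77 when the reference arm has the same p.

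**Direction.** By the identity, the ratio shrinks only if time at risk / total exposure is lower in the higher-rate arm. Two constructed examples use the planned arm sizes of 140 (placebo) and 280 (400 mg).

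1. *Different event timing.* All patients are exposed for 1 year. Placebo has 42 events at 0.1 year: SAP rate 42/140 = 30.0; time at risk 42 × 0.1 + 98 = 102.2, rate 41.1. The 400 mg arm has 105 events at 0.8 year: SAP rate 105/280 = 37.5; time at risk 105 × 0.8 + 175 = 259, rate 40.5. Ratio: SAP 1.25, time at risk 0.99.
2. *Discontinuation after the event.* All events occur at 0.4 year, and patients with an event on 400 mg stop IMP at 0.45 year. Placebo: SAP rate 30.0; time at risk 42 × 0.4 + 98 = 114.8, rate 36.6. The 400 mg arm: exposure 105 × 0.45 + 175 = 222.25, SAP rate 47.2; time at risk 105 × 0.4 + 175 = 217, rate 48.4. Ratio: SAP 1.57, time at risk 1.32.

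In both examples the SAP rate enlarges the difference between arms.

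**The case against.** The measure is fully disclosed: the formula is printed, exposure is defined, and the SAP nowhere calls it a hazard. It is one of several displays. The percentage of patients is shown, the event-based rate uses the right denominator, and the 52-week Kaplan-Meier curve is a proper time-at-risk analysis. Safety summaries are descriptive (Protocol 11.4.3; SAP 2.4.5). All of this stands, and it limits the weight of the point. It does not close the gap. The curve covers one composite over 52 weeks, so any hypoglycemia, the 18-week period and the subgroup rates have no time-at-risk summary. The 18-week period is the one in which Lantus is meant to be held stable.

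A reader might go further and infer that the rate must shrink the difference between arms and so hide an excess on sotagliflozin. The documents do not support that. Shrinkage is usual when timing and exposure are similar, but the two examples above reverse it. Equal timing cannot be taken for granted when Lantus titration resumes after Week 18 (Protocol 8.2.1.3). Nor do the documents establish an excess: Protocol 4.5 anticipates that an insulin-sparing effect could lower hypoglycemia risk, in which case shrinkage would understate a benefit. A reader might also take incidences of 30-50% as given. The documents state none, and for rare severe events the effect is negligible.

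**Conclusion.** The point holds for the level of the rate: it understates the first-event rate whenever patients remain exposed after a first event. The understatement passes about 10% only from roughly 20% incidence, assuming a constant hazard and full follow-up. The true size cannot be stated, because incidence is not documented and a constant hazard is doubtful across the change in insulin management at Week 18. For the comparison between arms, the supportable statement is conditional: movement toward no difference if timing and exposure are similar, and either direction if they are not. No hypothesis test, error rate, power or sample size is affected. The change is worth making chiefly for the common categories.

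**What to change.** In SAP 2.4.5.1, for the patient-based rate only, define the denominator as the sum over patients of time from first IMP dose to the first event of the category being tabulated, or to the end of the relevant treatment-emergent period if there is none. Keep total exposure for the event-based rate. State the denominator in the label of each rate. Apply this to the 18-week, 52-week and subgroup tables.

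No new data are needed, since onset date and time are already recorded (Protocol 10.6.1). There is some derivation work. The existing time-to-event variable serves only the 52-week composite, so first-event times are needed for each category and both periods. SAP 2.5.3 limits onset-date imputation to classifying events, so a simple rule is also needed for placing a first event with a partial onset date.

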2.4.5 Analyses of safety data

The summary of safety results will be presented by treatment group. The safety data except hypoglycemia will be summarized for the entire 52-week double-blind treatment period. The hypoglycemia will be summarized for the 18-week randomized core treatment period and the entire 52-week double-blind treatment period (see [Section 2.4.5.1](#)).

The “observation period” defined in [Section 2.1.4](#) is applicable in all safety analyses for the classification of AEs, determination of treatment-emergent Potentially Clinically Significant Abnormality (PCSA) values and the last on-treatment value for the laboratory, vital sign and ECG.

General common rules

All safety analyses will be performed on the safety population as defined in [Section 2.3.2](#), unless otherwise specified, using the following common rules:

- Safety data in patients who do not belong to the safety population (eg, exposed but not randomized) will be listed separately
- The baseline value (with the exception of serum creatinine and eGFR) is defined as the last available value before the first dose of double-blind IMP. For serum creatinine and eGFR, the baseline value is defined as the average of all values before the first dose of double-blind IMP.
- PCSA values are defined as abnormal values considered medically important by the Sponsor according to predefined criteria/thresholds based on literature review and defined by the Sponsor for clinical laboratory tests, vital signs, and ECG [[Appendix A](#)].
- PCSA criteria will determine which patients had at least 1 PCSA during the treatment-emergent adverse event period, taking into account all evaluations performed during the treatment-emergent adverse event period, including nonscheduled or repeated evaluations. The number of all such patients will be the numerator for the treatment emergent PCSA percentage
- The treatment-emergent PCSA denominator by group for a given parameter will be based on the number of patients assessed for that given parameter in the treatment-emergent adverse event period by treatment group on the safety population.
- For laboratory parameters cited in the protocol as efficacy endpoints (including HbA1c and plasma glucose, etc.), PCSA summaries will not be provided. These parameters will be summarized in [Section 2.4.4](#).

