Hypoglycemia	Safety	Follow safety guidelines Number (%) of patients with any hypoglycemia, severe hypoglycemia, documented symptomatic hypoglycemia during TEAE period of 18-week randomized core treatment period and entire 52-week double-blind treatment period, and incidence rates in 100 patient-years.		Severe hypoglycemia or documented symptomatic hypoglycemia by subgroups: race, age, gender, SU use at Week -1	KM plot time to first event of severe hypoglycemia or documented symptomatic hypoglycemia Summary of frequency/events of documented symptomatic hypoglycemia by hour during the TEAE period Documented symptomatic hypoglycemia maybe presented by <54 mg/dL (3.0 mmol/L) as appropriate.
Adverse Events	Safety	Follow safety guidelines	No	Common TEAEs by subgroups: race, age, gender, SU use at Week -1, baseline SBP, baseline eGFR	
Clinical laboratory data	Safety	Follow safety guidelines	Descriptive	No	No
Vital signs	Safety	Follow safety guidelines	Descriptive	No	No
ECG, Physical examination	Safety	Follow safety guidelines	Frequency summary	No	No

Statistical Analysis Plan

Version: Final 2.0
Lexicon Pharmaceuticals Protocol No. EFC14868

Date of Issue: 04 December 2019
Covance Study ID:000000155200

CGM SUB-STUDY ANALYSIS

Endpoint	Analysis population	Primary analysis	Supportive analysis	Subgroup analysis	Other analyses
CGM sub-study primary endpoint					
Percentage of time within the target glucose range of 70 to 180 mg/dL over 24 hours: Change from baseline to Week 19, (sotagliflozin 400 mg vs placebo)	CGM	ANCOVA (with missing values imputed by the retrieved dropouts imputation method or by washout MI method under MNAR framework): treatment, randomization stratum (HbA1c / SBP/SU use at Week -1), and country as fixed effects, and baseline CGM percentage value as a covariate	No	No	Summary statistics for observed values and changes from baseline by visit. Graphical presentations for mean changes from baseline (\pm SE) and mean values (\pm SE) by visit.
CGM sub-study secondary endpoints					

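### For patients treated beyond Visit 12, the SAP's hypoglycemia exposure formula contradicts its own 18-week period; programmed literally, it would give 18-week rates about 0.35 to 0.40 of the correct value

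*SAP*

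**What the plan says.** SAP 2.4.5 (Analyses of safety data) reports most safety data for 52 weeks only, but makes an exception here: "The hypoglycemia will be summarized for the 18-week randomized core treatment period and the entire 52-week double-blind treatment period". Appendix C lists the same two periods together with the rates: "TEAE period of 18-week randomized core treatment period and entire 52-week double-blind treatment period, and incidence rates in 100 patient-years".

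SAP 2.4.5.1 defines a special 18-week TEAE period with two cases:

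- Case (1), early stoppers: the period runs "up to 1 day after the last administration of IMP if the patient discontinued treatment on or before Visit 12".
- Case (2), patients still on treatment: it is "the time from the first administration of the double-blind IMP to the administration at Visit 12/Week 18", with Day 126 as the fallback when that date is missing. No extra day is added.

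Two rates are planned, one counting patients with an event and one counting events. Both use the same denominator; the event rate is "calculated as the total number of events / total exposure in 100 patient-years". Exposure is then explained once, for both periods: "Note: here exposure (in days) is the duration of TEAE period, ie, duration of IMP treatment in days +1". The note refers the reader to SAP 2.1.4, where the general TEAE period for hypoglycemia ends one day after the last dose.

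SAP 2.4.3.1 supplies the meaning of IMP duration: "Duration of IMP exposure is defined as last dose date of double-blind IMP" minus the first dose date, plus 1 day. Nothing there cuts it at Week 18.

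**The concern.** The note's two halves agree in two situations and disagree in a third. In the 52-week analysis, and for anyone who stops by Visit 12, the TEAE period is IMP duration plus one day. For a patient who continues past Visit 12, the 18-week TEAE period stops near Day 126, while IMP duration runs on to the last dose, as late as Week 52. Under the formula, events would be counted over 18 weeks and divided by up to a year of exposure. This affects patients with complete dates, so it is not a missing-data matter.

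The 18-week rate matters because Lantus is meant to be held stable until Week 18, so that study drug is assessed on constant background insulin (Protocol 4.4). Protocol 11.4.3 asks for safety analyses over both periods, and 11.4.3.2 asks for hypoglycemia rates in patient-years. SAP 2.4.5.1 also plans the rates by gender, age, race and sulfonylurea use, so a wrong denominator would carry into the subgroup tables. It would be hard to see in the output, since counts and percentages would still be right.

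**Working it through.** The documents state no hypoglycemia rate or exposure total, so there is no planned figure to reproduce. The check is person-time arithmetic.

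**Inputs from the documents**

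- Week 18 target: Day 126, visit window ±3 days, so Day 123 to 129 (Protocol 1.2; SAP 2.5.4).
- Week 52 target: Day 364, window Day 357 to 371 (Protocol 10.1).
- IMP duration: last dose − first dose + 1 (SAP 2.4.3.1).
- Hypoglycemia tail after the last dose: 1 day (SAP 2.1.4).

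**Formula.** Literal rate / correct 18-week rate = (18-week TEAE days) / (IMP duration + 1). The event count and the days-per-year constant cancel.

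**52-week completer.** IMP duration = 364 − 1 + 1 = 364 days, so literal exposure = 365 days. Correct 18-week exposure = 126 − 1 + 1 = 126 days.

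- Ratio = 126/365 = 0.345; equivalently, the literal denominator is 365/126 = 2.90 times too large.
- Across the visit windows: 123/372 = 0.331 to 129/358 = 0.360.

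**Patients who stop between Week 18 and Week 52.**

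- Last dose Day 127: 126/128 = 0.984
- Last dose Day 182: 126/183 = 0.689
- Last dose Day 273: 126/274 = 0.460

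**Group level.** The documents give no discontinuation rates, so these are assumptions: a fraction *a* stops before Week 18 with last dose at Day 63 (64 days of exposure), a fraction *b* stops after Week 18 with last dose at Day 245 (246 days), and the rest complete.

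Ratio = [64*a* + 126(1 − *a*)] / [64*a* + 246*b* + 365(1 − *a* − *b*)]

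| *a* | *b* | Correct mean days | Literal mean days | Ratio |
|---|---|---|---|---|
| 0 | 0 | 126.0 | 365.0 | 0.345 |
| 5% | 5% | 122.9 | 344.0 | 0.357 |
| 10% | 10% | 119.8 | 323.0 | 0.371 |
| 20% | 20% | 113.6 | 281.0 | 0.404 |

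**Illustration (assumed 140 completers, 100 events by Week 18, 365.25 days per year).**

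- Correct: 100 / (140 × 126/365.25) × 100 = 207.1 events per 100 patient-years.
- Literal: 100 / (140 × 365/365.25) × 100 = 71.5.

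**What drives the error.** If IMP duration were cut at Week 18 and only the extra day kept, the ratio would be 126/127 = 0.992, an error of 0.8%. Almost all of the discrepancy comes from not cutting at Visit 12.

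**The case against.** The strongest reply is that the note begins correctly. Its leading words set exposure equal to the length of the TEAE period, and the same section has just defined that period for the 18-week analysis, ending it at the Visit 12 dose. SAP 2.1.4 also sends the reader to 2.4.5.1 for the 18-week period. Read that way, the denominator is right and the formula is a loose gloss on the general case. This stands: a reader might infer that the SAP commits the trial to wrong 18-week rates, and the text does not support that. The error depends on programming the formula instead of the definition before it.

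The reply does not remove the contradiction. The formula is offered as the meaning of the phrase, it is the only expression of exposure given for these rates that can be coded directly, and no other part of the SAP gives an 18-week version.

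Two other strong readings also fail. One is that every patient treated past Week 18 is understated by two thirds: that figure belongs to 52-week completers, and late stoppers are affected less. The other is that the between-arm comparison would be materially distorted. With 8% stopping before Week 18 in both arms and the same mid-period days, 5% versus 20% stopping later gives ratios of 0.361 and 0.382, a shift of about 6% in the rate ratio. With 5% versus 10% (0.361 and 0.368) it is about 2%. These splits are assumed; the documents support neither.

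It is also fair to say that the safety analyses are descriptive and that no efficacy test depends on this.

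**Conclusion.** The exposure note in SAP 2.4.5.1 is internally inconsistent for one analysis: the 18-week rates of patients treated beyond Visit 12. If the formula is used as written, those rates come to 0.345 of the correct value for 52-week completers (0.331 to 0.360 across visit windows). At group level the ratio is about 0.35 to 0.40, on the assumption of 0 to 20% stopping in each part of the study at mid-period. If the period definition is used instead, the rates are correct. Hypoglycemia counts, percentages and all 52-week rates are unaffected under either reading.

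This should be corrected before programming. A near-threefold difference in a planned rate should not depend on which half of a sentence is coded.

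**What to change.** Replace the note in SAP 2.4.5.1 with explicit exposure definitions:

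- **52-week analysis, all patients:** IMP duration + 1, that is (last dose date − first dose date + 1) + 1.
- **18-week analysis, patients who stopped IMP on or before Visit 12:** the same formula.
- **18-week analysis, patients treated beyond Visit 12:** (Visit 12 date, or Day 126 if missing) − first dose date + 1, with no extra day.

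This adds no new rule; it writes out the SAP's own cases (1) and (2). In the same paragraph, case (1) gives its Day 126 fallback by reference to a Visit 18 date. The schedule ends at Visit 16, so this should read Visit 12. That is a separate slip and adds no weight to the exposure point.

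The cost is one SAP sentence, one derived variable and one corrected visit number. No data collection changes.
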